597 2. Participants can be withdrawn from the trial at the discretion of the Investigator due to
 598 safety concerns of if judged to be non-compliant with the trial protocol.

599 3. Pregnancy or intention of becoming pregnant

600 4. If target treatment dose of the randomized product is not tolerated by the subject.

601 5. If the trial investigator suspects acute pancreatitis, the trial drug will be discontinued until
 602 the confirmatory tests (clinically indicated laboratory and imaging) have been conducted
 603 and appropriate treatment has been administered. We anticipate confirmation within 72
 604 hours. If acute pancreatitis is confirmed, the participant will be withdrawn from the trial.
 605 If acute pancreatitis is not confirmed, the participant will resume the trial drug at the
 606 same dose previously used before temporary discontinuation.

607 6. Temporary trial drug discontinuation criteria:
 608 - Side effects to trial medication (until such side effects have resolved or have
 609 been otherwise addressed)
 610 - Acute illness requiring treatment or hospitalization
 611 - The longest time that the subject can be off trial drug and still continue in the trial
 612 is 4 weeks. If the trial drug is discontinued for >72 hours, then the dosing
 613 escalation regimen will be restarted at 0.6 mg daily and titrated up according to
 614 prescribing information recommendations.

616 **Subject Replacement**

617 Participants will not be replaced if they withdraw or become ineligible but they will be asked to
 618 return at the end of the trial period to complete the follow-up imaging/laboratory testing and
 619 analyzed in an intention to treat analysis. As up to a 28% drop-out rate is anticipated, enrolment
 620 will account for expected drop-out to minimize loss to follow-up given that subjects will not be
 621 replaced.

623 **Rationale for Trial Population**

624 The trial population represents the target population for which liraglutide is approved for chronic
 625 weight management in adult patients, with the additional inclusion criterion of a diagnosis of
 626 metabolic syndrome. This important criterion has been selected to enrich the trial population
 627 with participants with a high visceral adipose tissue burden in order to improve the statistical
 628 power to observe a meaningful effect on visceral adipose mass and enrich the trial population
 629 with individuals at high risk for cardiovascular disease.

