1108 irrespective of meals. However, it is preferable that liraglutide be injected during the same

1109 overall time period on a day to day basis. Subjects will be instructed to perform an air shot
 1110 before the first injection with the pen-injector. For further information, please see the direction
 1111 for use (DFU) for the liraglutide pen-injector. These DFUs will be provided together with the trial
 1112 product. The Investigator or trial staff will instruct subjects in how to inject liraglutide or placebo,
 1113 and will ensure that the subjects are familiar with the DFU. It will be documented in the subject's
 1114 research record that the subject has been instructed in the use of the pen-injector.

1115
 1116 Subjects will follow a fixed dose escalation and in order to reduce the level of side effects,
 1117 liraglutide is gradually escalated up to the maintenance dose. Subjects will be instructed to
 1118 escalate the liraglutide (active or placebo) dose to 3.0 mg/day over a 4 week period following an
 1119 initial dose of 0.6 mg/day and weekly dose escalation steps of 0.6 mg/day.

1120 If subjects do not tolerate an increase in dose during dose-escalation, the Investigator will have
 1121 the option to delay the next dose escalation for approximately one week. All subjects must be at
 1122 the target dose 3.0 mg or placebo at the latest 8 weeks after randomization.

1123
 1124 Dose escalation schedule:

Week	Dose (mg)
0	0.6
1	1.2
2	1.8
3	2.4
4 and beyond	3.0

1125
 1126 After reaching the target dose, 3.0 mg liraglutide or placebo dose and dosing frequency should
 1127 not be changed at any time during the treatment period. If any dose is missed by the subject up
 1128 to and including 3 consecutive days it will be documented in the research record and the
 1129 Investigator will discuss the importance of treatment compliance with the subject. After a
 1130 potential discontinuation up to 3 days the subject must be re-initiated on trial drug on target
 1131 dose 3.0 mg liraglutide or placebo. Missed doses for more than 3 consecutive days will be
 1132 discussed with the PI and it will be up to Investigator's judgment if the subject can continue on
 1133 target dose or should be withdrawn.

1134
 1135 It is always important that the Investigator emphasizes to subjects the necessity of compliance
 1136 with regard to taking trial drug as described in the protocol. It is the responsibility of the

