 1137 Investigator to access the subject's overall compliance throughout the trial and subjects deemed
 1138 to be non-compliant subjects may be withdrawn at the Investigator's discretion. If subjects do
 1139 not tolerate the target dose, they will be withdrawn from the trial. If the Investigator suspects
 1140 acute pancreatitis, all suspected drugs will be discontinued until confirmatory tests have been
 1141 conducted. If tests reveal that a subject does not have acute pancreatitis, the subject can
 1142 remain in the trial with re-initiation of titration until the target dose is reached.

1143
 1144 **Packaging and Labelling of Trial Medication(s)**

1145 All trial products will be packed and labeled by Novo Nordisk and provided in non-subject
 1146 specific boxes. Labeling will be in accordance with local law and trial requirements.

1147
 1148 **Storage and Drug Accountability of Trial Medication(s)**

1149 The Investigator must keep track of all received, used, partly used and unused trial products by
 1150 the use of the drug accountability module in the computerized randomization system.

1152 Store in a refrigerator (2°C to 8°C). Do not store in the freezer or directly adjacent to the
1153 refrigerator cooling element. Do not freeze liraglutide/ placebo and do not use liraglutide/ placebo
1154 if it has been frozen. Liraglutide/ placebo should not be used if it does not appear clear and
1155 colorless. After first use of the liraglutide/ placebo pen, the product can be stored for 30
1156 days at room temperature (+15°C to +30°C)/(59°F to 86°F) or in a refrigerator (+2°C to
1157 +8°C)/(+36°F to +46°F). Keep the pen cap on when liraglutide/ placebo pen is not in use in
1158 order to protect from light. Liraglutide/ placebo should be protected from excessive heat and
1159 sunlight. Always remove the injection needle after each injection and store the liraglutide/ placebo
1160 pen without an injection needle attached. This prevents contamination, infection, and
1161 leakage. It also ensures that the dosing is accurate. No trial product which has exceeded the
1162 expiry date must be used.

1163
1164 The Investigator will ensure the availability of proper storage conditions and record and evaluate
1165 the temperature. The temperature will be recorded and evaluated on a daily basis (working
1166 days) using as a minimum a calibrated min/max thermometer. A log to document the

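### The protocol gives conflicting restart doses after a negative pancreatitis work-up and after more than 72 hours off trial drug

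*Protocol*

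**What the plan says.** **Negative pancreatitis work-up.** Withdrawal Criteria item 5: "If acute pancreatitis is not confirmed, the participant will resume the trial drug at the" dose in use before the interruption. The item expects the work-up to take up to 72 hours but does not make the restart rule depend on that. Near the end of Trial medication(s) / devices(s), for the same event, the subject can "remain in the trial with re-initiation of titration until the target dose is reached". No duration and no starting dose are given there.

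**Longer gaps.** Withdrawal Criteria item 6 allows up to 4 weeks off drug. Beyond 72 hours, the "escalation regimen will be restarted at 0.6 mg daily and titrated up according to" the prescribing information. Trial medication(s) / devices(s) covers subjects who have reached target. After a "potential discontinuation up to 3 days the subject must be re-initiated on trial drug on target" dose. It then says "Missed doses for more than 3 consecutive days will be" taken to the principal investigator, and the investigator judges whether the subject continues on "target dose or should be withdrawn". The same paragraph says that, once target is reached, dose and frequency should "not be changed at any time during the treatment period".

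**Reason for escalation.** Trial medication(s) / devices(s): "Subjects will follow a fixed dose escalation and in order to reduce the level of side effects".

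**The concern.** A restart dose is an instruction that staff carry out on the day, so two sections that differ cannot both be obeyed. Take a subject at 3.0 mg who has been off drug for 5 days because of an acute illness. Item 6 restarts that subject at 0.6 mg. Trial medication(s) / devices(s) keeps the subject at 3.0 mg or withdraws the subject, and does not mention re-titration.

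Three things are at stake:

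- **Tolerability.** Returning to 3.0 mg after a long gap bypasses the gradual escalation that the protocol adopts to limit side effects. Its background section reports nausea in 47.6% and vomiting in 16.5% of patients on 3.0 mg in an earlier trial.
- **Retention.** Subjects who cannot tolerate the target dose are withdrawn, and one section allows withdrawal after a gap that the other accepts for up to 4 weeks.
- **Consistency of exposure and of compliance.** Similar subjects may be dosed differently after similar interruptions. The secondary per-protocol analysis (Evaluability of Subjects) needs a view of what correct dosing was, and here following one rule breaks the other.

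**Working it through.** No statistical figure in the protocol is in question, so the check sets the rules side by side and then sizes the difference in dose. A gap of 72 hours and one of 3 days are treated as the same threshold.

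| Situation | Withdrawal Criteria | Trial medication(s) / devices(s) | Compatible? |
|---|---|---|---|
| Negative work-up, 72 h or less, at 3.0 mg | Item 5: 3.0 mg | Re-titrate; its own rule for gaps up to 3 days says 3.0 mg | No |
| Negative work-up, 72 h or less, still escalating | Item 5: previous dose | Re-titrate, start not stated | Possibly: resume and keep escalating |
| Negative work-up, over 72 h | Item 5: previous dose; item 6: 0.6 mg | Re-titrate, start not stated | Items 5 and 6 conflict as worded, unless the previous dose was 0.6 mg |
| Gap over 72 h and up to 4 weeks, at 3.0 mg | Item 6: 0.6 mg | Continue at target or withdraw | No |

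**Inputs** (dose escalation schedule, Trial medication(s) / devices(s)): 0.6, 1.2, 1.8 and 2.4 mg/day for one week each, then 3.0 mg/day; 40 weeks on treatment. Item 6 refers re-titration to the prescribing information, so using these weekly steps for it is an assumption.

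**Restart dose**

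- At target, gap over 72 hours: 3.0 / 0.6 = 5-fold.
- Still escalating, item 5 against item 6 only: 0.6, 1.2, 1.8 or 2.4 mg divided by 0.6 mg = 1, 2, 3 or 4.
- Item 5 against the re-titration sentence: no ratio can be given, because that sentence states no starting dose.

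**Exposure over the four weeks after the restart**

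- Re-titration: 7 × (0.6 + 1.2 + 1.8 + 2.4) = 7 × 6.0 = 42 mg.
- Target dose: 28 × 3.0 = 84 mg.
- Shortfall: 84 − 42 = 42 mg, or 50%.

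**Against the whole treatment period**

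- Planned dose: 42 + 36 × 7 × 3.0 = 42 + 756 = 798 mg.
- 42 / 798 = 5.3%. This is the most that one re-titration costs; the loss is smaller if it begins in the last four weeks.

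**The case against.** The best defence separates the rules by cause and by length of gap. Item 6 stands under temporary discontinuation for side effects or acute illness, whereas the three-day rules in Trial medication(s) / devices(s) concern doses the subject misses and speak of compliance. Likewise, item 5 is written around a short work-up and item 6 follows directly with the rule for longer gaps, so the two can be read in sequence. A subject still escalating can satisfy both pancreatitis instructions by resuming the previous dose and continuing upward. Finally, the trial is double-blind, the same rules apply to both arms and the primary analysis is by intention to treat, so uneven exposure need not bias the comparison.

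Part of this stands. The pancreatitis conflict for short work-ups is clear-cut only at target dose, reading items 5 and 6 in sequence is reasonable though not stated, and no bias is shown.

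The split by cause does not hold. The 72-hour sentence in item 6 is not limited to any cause. Trial medication(s) / devices(s) itself calls a gap of up to 3 days a discontinuation. A subject off drug for 5 days through illness or side effects has also missed more than 3 consecutive days of doses, so both rules apply to that subject. The tolerability reason for escalating does not depend on why doses were missed either. For a subject at target with a short negative work-up, no reading reconciles the two instructions.

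**Conclusion.** The concern holds and should be fixed. The restart instructions conflict for a subject at target with a negative pancreatitis work-up of 72 hours or less, and for a subject at target who is off drug for more than 72 hours. As worded, items 5 and 6 also conflict when a work-up overruns 72 hours.

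The largest consequence is the five-fold difference in restart dose after a longer gap, which is a matter of subject safety and tolerability. The loss of exposure is modest: at most 5.3% of the planned dose per re-titration, assuming the protocol's weekly steps. The number of subjects affected is unknown, because the protocol gives no rate of interruptions. Sample size, power, alpha and the primary intention-to-treat comparison are unchanged.

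**What to change.** Adopt one rule based on time off drug and word it identically in Withdrawal Criteria items 5 and 6 and in Trial medication(s) / devices(s). For example:

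- **72 hours or less**, including a negative pancreatitis work-up: resume at the previous dose.
- **More than 72 hours and up to 4 weeks**, whatever the reason: restart at 0.6 mg and re-titrate.
- **More than 4 weeks**: stop trial drug, and still invite the subject to Visit 16x at week 40 as Visit Procedures provides.

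In Trial medication(s) / devices(s), delete the option to continue at target after more than 3 days, and replace the re-titration sentence on pancreatitis with a reference to the single rule. Say that re-titration is an exception to the ban on dose changes after target, and that the 8-week deadline for reaching 3.0 mg applies to the initial escalation. The sponsor may prefer another rule, provided there is only one.

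The cost is amendment wording and retraining of staff at a single center.

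### The dosing rules contradict each other for a subject at 3.0 mg who misses more than 72 hours of drug, and again after suspected pancreatitis is not confirmed

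*Protocol*

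**What the plan says.** Two sections of the Protocol govern what happens after an interruption.

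**Withdrawal Criteria.** Item 6 deals with temporary discontinuation. It lists side effects and acute illness, then says that the longest time off drug compatible with staying in the trial "is 4 weeks. If the trial drug is discontinued for >72 hours, then the dosing" "escalation regimen will be restarted at 0.6 mg daily and titrated up according to" the prescribing information. Item 5 deals with suspected acute pancreatitis: drug is stopped while tests are done, an answer is expected within 72 hours, and if the diagnosis is not confirmed the subject goes back to the dose taken before the stop.

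**Trial medication(s) / devices(s).** All subjects must reach "the target dose 3.0 mg or placebo at the latest 8 weeks after randomization". From then on, dose and frequency should "not be changed at any time during the treatment period". After a "potential discontinuation up to 3 days the subject must be re-initiated on trial drug on target" dose. For longer gaps: "Missed doses for more than 3 consecutive days will be" "discussed with the PI and it will be up to" the Investigator to judge whether the subject stays on "target dose or should be withdrawn". Later in the same section, a subject whose tests rule out acute pancreatitis may stay in the trial, with titration started again until the target is reached.

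**The concern.** These are operative dosing instructions, and staff who follow one of them depart from the other. The medication section gives the reason for gradual escalation as limiting side effects. That reason also applies after a gap long enough for item 6 to require a new escalation, whatever caused the gap.

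Interruptions are foreseeable. Item 6 names side effects as a ground for pausing, and the background section reports nausea in 47.6% and vomiting in 16.5% on 3.0 mg in an earlier trial. Item 4 of the Withdrawal Criteria withdraws subjects who cannot tolerate the target dose. A poorly tolerated return straight to 3.0 mg could therefore end in a withdrawal that re-titration is meant to avoid.

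**Working it through.** **Rules side by side, for a subject already at 3.0 mg**

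| Situation | Withdrawal Criteria | Trial medication section |
|---|---|---|
| Gap up to 72 h (3 days) | Item 6 requires no restart at 0.6 mg | Resume 3.0 mg |
| Gap over 72 h, up to 4 weeks | Item 6: restart at 0.6 mg, re-titrate | 3.0 mg or withdrawal |
| Pancreatitis not confirmed | Item 5: previous dose (3.0 mg) | Start titration again; no starting dose named |

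*First conflict (second row).* 72 h / 24 = 3 days, so the two sections use nominally the same boundary. Beyond it, the step that item 6 makes mandatory is not among the medication section's options. The ratio of the two restart doses is 3.0 / 0.6 = 5.

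*Second conflict (third row).* Neither pancreatitis rule depends on the length of the gap.
- Work-up of up to 72 h: item 5 agrees with item 6 and with the medication section's own rule for gaps of up to 3 days. The medication section's pancreatitis sentence is the outlier.
- Work-up beyond 72 h, which is possible because 72 h is only anticipated: item 5 also conflicts with item 6.
- A subject still escalating could resume the prior dose and continue upward, which satisfies both. The conflict concerns subjects already at target.

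**Size of the exposure difference per affected active-arm subject.** Inputs: weekly 0.6 mg steps, 3.0 mg from week 4, 40 treatment weeks (medication section, dose escalation schedule).
- Four escalation weeks: 7 × (0.6 + 1.2 + 1.8 + 2.4) = 42 mg
- The same four weeks at 3.0 mg: 28 × 3.0 = 84 mg
- Cost of re-titration: 84 − 42 = 42 mg
- Planned total: 42 + 36 × 7 × 3.0 = 798 mg; 42 / 798 = 5.3%
- Days below target: 28 of 40 × 7 = 280, or 10%

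The full 42 mg applies if the restart begins by week 40 − 4 = 36, and less applies after that. Drug missed during the gap is lost under either rule and is not counted.

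**The 8-week limit.** The earliest day at 3.0 mg is day 28. A gap of more than 3 days and 28 days of re-titration bring the subject back to 3.0 mg only after day 28 + 3 + 28 = 59. The limit is day 8 × 7 = 56. No restart from 3.0 mg under item 6 can meet it.

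**Where the 72 hours start.** With daily injections, three missed doses put 4 × 24 = 96 h between consecutive injections, but only 72 h between the first missed dose and the next injection. Counted from the last injection, three missed doses already exceed item 6's threshold while the medication section still requires 3.0 mg. The Protocol does not say which count applies.

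**The case against.** The best reply to the first conflict is that the rules cover different events. Item 6 sits under temporary discontinuation, beside side effects and acute illness. The medication section speaks of doses the subject misses and of counselling on compliance. A site could apply the first to medical pauses and the second to non-adherence. This softens the conflict but does not remove it. Item 6's sentence on gaps over 72 hours names no cause, the medication section itself uses the word discontinuation, and its ban on changing the dose has no exception for medical pauses. The reply does nothing for the second conflict.

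It is also fair that the hazard is gated. A reader might infer that the Protocol orders 3.0 mg after a long gap. It does not: the medication section permits it, after discussion with the PI and at the Investigator's judgment, with withdrawal as the alternative. What remains is that this section gives neither of them the 0.6 mg restart that item 6 mandates.

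**Conclusion.** The dosing rules contradict each other as written, in two places, and nothing in the Protocol sets an order of precedence. The point should be corrected, because it concerns tolerability and uniform dosing.

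The size is a factor of 5 in restart dose after a gap of more than 72 hours. Choosing re-titration costs an affected active-arm subject 42 mg (5.3%) and 28 days below target. Those figures assume the Protocol's own weekly steps with no delayed step and a restart by week 36; item 6 refers to prescribing information that is not at hand.

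A reader might go further and infer a 5.3% loss of exposure across the active arm, or a biased primary result. The document supports neither. It gives no rate of gaps over 72 hours, so the number of subjects affected is unknown, and the restart rule does not change the arm in which a subject is analysed under intention to treat.

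**What to change.** Make the medication section subject to Withdrawal Criteria item 6, and use one rule in both sections, including for unconfirmed pancreatitis:

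- Gap up to 72 hours: resume the prior dose.
- Gap over 72 hours and up to 4 weeks: if the subject continues, restart at 0.6 mg and re-titrate.
- Gap over 4 weeks: the subject does not continue in the trial, as item 6 already states, and is invited to Visit 16x (Visit Procedures).

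Keep the PI discussion and the Investigator's discretion to withdraw. State that the 8-week limit for reaching 3.0 mg applies to the first escalation. Define when the 72 hours start.

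The cost is a short protocol amendment with IRB review, editing item 5 of the Withdrawal Criteria and the medication section and adding the definition of the 72 hours, with a note to site staff. No scheduled visits are added, and unscheduled dispensing is already provided for under Visit Procedures. The price in treatment is that subjects who restart spend about 4 weeks below the target dose.
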